¹⁴ DXA scans should be performed for all subjects as indicated. The initial DXA scan may be scheduled for any time before the first day of study drug and will be considered the baseline measurement for the bone mineral density endpoint and body composition assessments. Subjects should not take calcium supplements within the 24 hours before a DXA scan.

¹⁵ Either the subject will pick up study drug in the clinic or the clinic will ship study drug will be shipped directly to the subject. Study drug will be taken daily between 6 PM and midnight, with an evening meal. The evening meal should contain approximately 25- <50% fat content. Study drug may be consumed up to 30 minutes after completing the evening meal, if necessary. (In Denmark, UK, Ireland, Romania, Estonia or Turkey shipping of study drug directly from clinic to subject's home is not permitted)

¹⁶ During the Treatment Period, sites will make telephone contacts to subjects who are eligible for a GC dose adjustment within 2 weeks after each applicable study visit and based on their A4 level at that visit. Subjects who are not eligible for a GC change will not be telephoned. The site will direct the subject to adjust his/her GC dose by no more than 5 mg/day HCe increments if the subject has not experienced any change in clinical status since the previous study visit. If a subject's GC dose is adjusted, the site will telephone the subject again 7 days after the GC dose adjustment to assess for the occurrence of AEs and the initiation of new concomitant medications. GC reductions may

begin at Week 2 (based on the Day 1 A4 measurement) and increases in GC dose may begin based on the A4 measurement at Week 6. GC dose may be reduced to a minimum of 15 mg HCe per day (approximately physiologic replacement level).

¹⁷ Bottles of HC for stress dosing (see [Section 4.1.4.4](#)) will be dispensed starting at Day 1 and thereafter as needed to replace opened bottles. Accountability for bottles of HC will be performed at every study visit.

¹⁸ Subjects will use an electronic study diary to document study drug and background GC adherence. Female subjects will also use the study diary to record menstrual information (including start and stop dates of menses).

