4.1.4 Procedures for Glucocorticoids

4.1.4.1 General Procedures for Glucocorticoids

Information to be collected at screening about a subject's current and historical GC therapy during the past year include the type(s) of GC, the regimen(s), reason(s) that the subject is/was on that particular GC regimen, and any GC stress dosing during the past year.

To be eligible to enter this study, subjects must be on a stable dose of GC replacement ≥ 30 mg/day and ≤ 60 mg/day in HCe for ≥ 1 month before screening without any evidence of non-adherence to the GC regimen during this period (stress dosing is allowed). For any subject whose prescribed total daily GC dose varies from day to day but is stable on a weekly basis, an average total daily dose based on the total weekly dose will be calculated to determine eligibility.

Subjects with the salt-wasting form of CAH must also be on a stable dose of mineralocorticoid replacement for ≥ 1 month before screening. A change to a subject's GC regimen during the study could necessitate an adjustment to the subject's mineralocorticoid regimen. The adequacy of a subject's mineralocorticoid dose should be monitored throughout the study and adjusted as needed to adequately maintain standing blood pressure, plasma renin levels, and electrolytes (serum potassium in particular) within acceptable ranges ([Speiser 2018](#)).

Please see instructions for administration of GCs through Week 24 and after Week 24 below.

Administration of GCs through Week 24:

- Participants who enter the study under protocol versions prior to Protocol Version 7.0 will receive Sponsor-supplied GCs
- Participants who enter the study under Protocol Version 7.0 and higher will receive Principal Investigator-prescribed GCs *
- Participants should remain on the same GC (not the same dose) through week 24. If a change is necessary due to drug shortage, etc., switching within the same type of GC (i.e., intermediate – intermediate/prednisone – prednisolone) is allowed. Any such changes should be discussed with the Medical Monitor.

*In countries where prednisolone 1mg is not commercially available, the Sponsor will provide this GC through week 24

Administration of GCs after Week 24:

- Participants who enter the study under any protocol version (1 and higher) will use Principal Investigator-prescribed GCs
- A change in GC type (e.g., prednisone to prednisolone) is acceptable after Week 24 (see note on change between types of GC below)

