4.1.4.4 Stress Dosing of Glucocorticoid

During times of clinically significant physical stress such as intercurrent illness with fever, surgical procedures, or significant trauma, subjects may take extra GC (in the form of HC) consistent with the “sick day guidelines” for prevention of adrenal crisis shown in [Table 2](#) ([Bornstein 2016](#)). Sites may employ variations on these guidelines, consulting with the Medical Monitor, if possible, in non-urgent situations. The Sponsor will provide all subjects with oral HC for the purposes of stress dosing ([Section 6.2.2](#)). For subjects who are not taking HC as their background GC regimen, the stress dose of HC should be estimated based on the relative potencies of GCs specified in [Table 1](#).

The stress doses recommended in [Table 2](#) are meant to *replace* a subject’s usual daily GC dose; they are NOT taken *in addition* to the subject’s usual daily GC dose. When taking the stress dose orally, the subject should take the entire stress dose using HC tablets from the bottle provided by the Sponsor. Daily replacement dosing from the subject’s or Sponsor-provided GCs should be temporarily held during stress dosing and reinstated as soon as the stress dosing period ends.

While all GC stress doses should be entered into the EDC, changes to usual daily GC dose only need to be entered into EDC when there is a definitive long-term, chronic alteration in the usual daily GC dosing regimen.

Table 2. Sick Day Guidelines for Stress Dosing of Hydrocortisone

Condition	Stress Dosing of Hydrocortisone
Home management of fever >38 °C (>100.4 °F) or illness requiring bed rest, when requiring antibiotics for an infection, or before undergoing a minor outpatient procedure (eg, dental work)	
 Approximately double the routine oral GC dose (and give as HC) until recovery (usually 2 to 3 days) For fever >39 °C (102.2 °F) only, approximately triple the routine oral GC dose (and give as HC) until recovery (usually 2 to 3 days)¹ Increase consumption of electrolyte-containing fluids and simple and complex carbohydrates (El-Maouche 2018), as tolerated
Unable to tolerate oral medication due to gastroenteritis or trauma	
 HC 100 mg IM or SC
Minor to moderate surgical stress	
 HC 25 to 75 mg/24 hours (usually 1 to 2 days)

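### The stress dose for minor to moderate surgery replaces the usual glucocorticoid dose but has no floor, so its low end is below every permitted entry dose

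*Protocol*

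**What the plan says.** Protocol 4.1.4.4 presents stress dosing as an addition: at times of physical stress, surgery included, "subjects may take extra GC (in the form of HC) consistent with the" sick-day guidelines in Table 2. The next paragraph makes the Table 2 doses a substitute for the usual daily dose, not a supplement to it. Background GC "should be temporarily held during stress dosing and reinstated as soon as the stress dosing period ends".

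Two rows of Table 2 matter here:

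- **Fever, illness or minor procedure.** The row covers home management of fever or illness, "or before undergoing a minor outpatient procedure (eg, dental work"). Its dose is "Approximately double the routine oral GC dose (and give as HC) until recovery (usually 2 to 3 days").
- **Minor to moderate surgical stress.** The dose is "HC 25 to 75 mg/24 hours (usually 1 to 2 days").

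On the usual dose, Protocol 4.1.4.1 states that "subjects must be on a stable dose of GC replacement ≥ 30 mg/day and ≤ 60 mg/day in HCe". On the lower limit of tapering, a footnote to the schedule in Protocol 1.3.4 says "GC dose may be reduced to a minimum of 15 mg HCe per day (approximately physiologic replacement level").

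On discretion, 4.1.4.4 adds: "Sites may employ variations on these guidelines, consulting with the Medical Monitor, if possible, in non-urgent situations". SAP 4.2.3 says that stress doses are taken on a physician's advice and gives no number. Neither document sets a minimum stress dose relative to the subject's usual dose.

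**The concern.** The first row of Table 2 scales with the subject's own dose. The surgical row is an absolute range. Because the tabulated dose replaces a held dose, an absolute range can fall below what the subject was already taking. The entry criteria guarantee this at the low end, since 25 mg is less than the 30 mg/day entry minimum. A site could comply with the table and lower GC exposure during surgery, although the section exists to raise it.

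The table is also internally inconsistent: dental work attracts a doubled dose, while a larger procedure may attract less than the routine dose.

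What is at stake is subject safety in a disease where the protocol itself treats adrenal crisis as a main hazard. Protocol 2.2.1 reports it as 42% of deaths in one cohort, and Protocol 7.1.5 and 8.3.8 have dedicated adrenal-insufficiency rules.

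**Working it through.** There is no power, sample-size or alpha figure to reproduce. The check is arithmetic on stated doses. Hydrocortisone (HC) has potency 1 in Protocol Table 1, so mg HC equals mg HCe.

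**Inputs.** Surgical row: 25 to 75 mg per 24 hours, replacing the usual dose (Protocol 4.1.4.4). Usual dose D at entry: 30 to 60 mg/day (4.1.4.1). First row of Table 2: about 2 × D. Approximately physiologic level: 15 mg/day (1.3.4).

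**Formulas.** Shortfall at the low end = D − 25. Relative shortfall = 1 − 25/D. Share of the 25–75 range below the usual dose = (D − 25)/50.

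| D (mg/day) | D − 25 (mg) | 1 − 25/D | (D − 25)/50 | 75/D | Dental work, 2 × D (mg) |
|---|---|---|---|---|---|
| 30 | 5 | 17% | 10% | 2.50 | 60 |
| 40 | 15 | 38% | 30% | 1.88 | 80 |
| 50 | 25 | 50% | 50% | 1.50 | 100 |
| 60 | 35 | 58% | 70% | 1.25 | 120 |

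**Within-table comparison.** 2 × D exceeds 75 when D > 37.5 mg/day. Above that dose, the dental-work dose is larger than even the top of the surgical row. The remaining rows give 100 mg by injection, or 100 mg followed by 200 mg/24 hours (falling to 100 mg/day after a crisis). All of these exceed 60 mg, so at entry doses the surgical row is the only one that can fall below the usual dose.

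**Against the physiologic level.** 25/15 = 1.67 and 75/15 = 5.0. The percentages in the table are therefore measured against a supraphysiologic dose and do not measure lost stress cover.

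**When the problem stops.** At D = 25 the ratio 25/D is 1.0; at 20 it is 1.25; at 15 it is 1.67. A subject entering at 30 mg/day reaches 25 after one 5 mg reduction. A subject entering at 60 needs (60 − 25)/5 = 7 reductions. The adjustment points are Day 1 (taking effect at Week 2) and Weeks 6, 12, 18, 24, 32 and 40, so 25 mg/day is reached no earlier than the Week 40 adjustment. Reductions also require androstenedione (A4) at or below the upper limit of normal (ULN), while entry allows up to 2.5 times that limit, so some subjects may not taper.

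**Effect on endpoints.** SAP 8.3.20.3 leaves stress dosing out of the total daily GC dose, so the primary endpoint is untouched. SAP 8.3.20.5 does count stress doses in cumulative GC dose (exploratory endpoint 3.2). In the largest entry-dose case, two days at 25 instead of 60 mg differ by 2 × 35 = 70 mg. Against 24 × 7 × 60 = 10,080 mg at an unchanged 60 mg/day, that is 0.7%.

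**The case against.** The strongest reply is that the section already answers the point. It speaks of additional GC for surgery, and a total below the usual dose is not additional, so a sensible reader would not give 25 mg to someone on 40 mg/day. The row is a range, the doses are recommendations, sites may vary them, and a physician advises. For every entry dose the usual dose already lies inside 25 to 75 mg. Protocol 2.2.2 accepts that physiologic doses may be enough to prevent adrenal insufficiency, and 25 mg exceeds the approximate physiologic level. Table 2 is attributed to a published guideline that was not available for this review.

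Most of this stands. A reduction is permitted, not required. No harm from 25 mg is shown. Whether the row or the replacement sentence is the misfit cannot be settled without the source. What does not follow is that the text is adequate: discretion is not a floor, and 25 mg complies with the table as written. The purpose statement and the dosing rule conflict, and a table meant to guide about 130 sites (Protocol 5) should not rely on readers to resolve that.

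Two objections to the remedy are also fair. A floor at the usual dose is still not an increase, and it leaves the mismatch with the dental-work row. In addition, the A4 algorithm sets no cap on increases: from 60 mg/day, a fourth 5 mg increase gives 80 mg/day, which would put the floor above the row's 75 mg top.

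**Conclusion.** The concern holds, as a minor point. At every permitted entry dose the low end of the surgical row is a cut of 5 to 35 mg (17% to 58%), and nothing in either document prevents a site from using it. This rests on the replacement sentence being applied as written and on the usual dose at the time of surgery being above 25 mg/day. It does not rest on any claim that 25 mg is clinically insufficient, which the documents neither show nor exclude. Exposure is brief, usually 1 to 2 days. The number of subjects affected is unknown, because neither a baseline dose distribution nor an expected number of procedures is given. The arithmetic and the conflict in the text are certain; the clinical consequence is not.

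**What to change.** Add one sentence to the surgical row and to the replacement paragraph in 4.1.4.4: *the total HC given per 24 hours must not be less than the subject's current total daily GC dose in HCe (Table 1)*. State that this floor prevails if the current dose is ever above 75 mg/day. For entry doses the floor is 30 to 60 mg, inside the row's own range, so the range itself can stay. Leave any increment above the floor to the treating physician and the Medical Monitor. They should also decide whether the row ought to be brought into line with the doubling rule for minor procedures; the floor alone does not do that.

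The floor works whichever of the two statements is at fault. The cost is one sentence in two places and a letter to sites, with no new data, procedures or subjects. Protocol 10.12 provides for Administrative Letters, of which investigators inform their IRB/EC, but does not define what qualifies. If a mandatory dosing minimum is judged to need full approval, send the site letter as a reminder that surgical stress dosing should not go below the usual dose, and put the rule in the next amendment.

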4.1.4.5 Post-Treatment Glucocorticoid Dosing

Upon completion of the Treatment Period, subjects will maintain the GC regimen and mineralocorticoid regimen (as applicable) established during the course of the study until the 30-day follow-up visit unless the Investigator determines that the subject's clinical status necessitates a dosing change. After completion of the study, GC therapy will be managed at the discretion of the subject's treating physician.

4.2 Scientific Rationale for Study Design

In previous Phase 2 open-label studies, tildacerfont exhibited an acceptable safety profile and proof-of-concept efficacy in reducing ACTH, 17-OHP, and A4 levels in adult subjects with classic CAH, which support the continued clinical development of tildacerfont. Study SPR001-204, which has a 24-week randomized, double-blind, Placebo-Controlled Treatment Period followed by a 52-week Open-Label period and will enroll approximately 90 subjects, will provide a more definitive, longer-duration, powered dataset. An optional Open-Label Extension Period will provide up to an additional 240 weeks of open-label treatment with tildacerfont at 200 mg QD. The placebo treatment group will control for any potential placebo effects in CAH and their impact on the overall tildacerfont treatment effect.

Given the problematic nature and significant side effects of standard-of-care CAH therapy using chronic supraphysiologic GC replacement (see [Section 2.2.2](#)), an important goal of treatment in CAH is the reduction of GC dose requirements ([Speiser 2018](#)). To that end, Study SPR001-204 will be the first clinical study to evaluate the potential GC-sparing effects of tildacerfont in subjects with CAH, with change in GC dose after 24 weeks of study drug as its primary endpoint and other measures of GC dose reduction as secondary endpoints. To evaluate tildacerfont's potential to reduce GC use in CAH, Study SPR001-204 will enroll subjects who are taking supraphysiologic doses of GCs (and have $LLD \leq A4 \leq 2.5 \times ULN$) and gradually reduce the GC regimen in subjects who maintain $A4 \leq ULN$ during the Treatment Period.

Study SPR001-204 will enroll subjects who are taking supraphysiologic doses of GCs and have $LLD \leq A4 \leq 2.5 \times ULN$. Based on subgroup analyses of data from previous Phase 2 studies, these subjects constitute an appropriate subpopulation of CAH patients for evaluating reductions in GC dose. Eligibility for the previous Phase 2 Studies SPR001-201 and SPR001-202 was based primarily on elevated 17-OHP. This contributed to the recruitment of a heterogeneous population of CAH patients that may have obscured the efficacy signal across different dose cohorts in these studies. When baseline A4 and ACTH levels were instead used to stratify subjects into subgroups, 2 distinct subgroups were revealed that differed by their mean background GC dose at study entry and tildacerfont PD response profiles. These 2 subgroups had potentially different treatment goals. The subgroup of subjects with elevated A4 and ACTH

showed greater, more consistent reductions in key hormones in response to tildacerfont treatment and would require reduction of key hormones before any GC dose reduction. In contrast, the subgroup of subjects with lower A4 and ACTH were on a higher mean GC dose and constitute an appropriate subpopulation of CAH patients for a study of GC reduction. Enrolling this subpopulation of CAH patients will provide a more homogeneous study population from which to draw more robust conclusions.

Study SPR001-204 will treat subjects with tildacerfont for up to 76 weeks, significantly longer than previous Phase 2 studies. The initial Phase 2 Study SPR001-201 treated subjects with tildacerfont for 2 weeks at each dose level ranging from 200 mg to 1000 mg per day. The subsequent Phase 2 Study SPR001-202 treated subjects with tildacerfont for 12 weeks at 400 mg QD. The magnitude of the efficacy response strengthened over 12 weeks of therapy, suggesting that the full treatment effect of tildacerfont may only be revealed after longer-term therapy. Study SPR001-204 will treat subjects with randomized study drug for 24 weeks during the Placebo-Controlled Treatment Period and with open-label tildacerfont for a further 52 weeks during the Open-Label Period. An optional Open-Label Extension Period will provide up to an additional 240 weeks of open-label treatment with tildacerfont at 200 mg QD. This duration of treatment will provide much longer-term monitoring of clinical outcomes for this chronic drug. The 30-day post-treatment washout period allows for adequate safety follow-up and analysis of any HPA axis rebound after the last dose of study drug.

Subjects cannot be on dexamethasone during this study because dexamethasone may have a moderate drug interaction with tildacerfont that would confound efficacy analysis. Based on nonclinical and Phase 1 clinical data, tildacerfont is a moderate inhibitor of CYP3A4. Dexamethasone is primarily metabolized through CYP3A4, and GC exposure data from Study SPR001-201 have shown a potential for drug-drug interaction (DDI) between tildacerfont and dexamethasone, with tildacerfont increasing dexamethasone exposures approximately 1.8-fold and with the lower bound of the associated 95% confidence intervals (CIs) generally above 1.0. In contrast, prednisone/prednisolone and HC are metabolized through multiple pathways, with CYP3A4 comprising <18% of its metabolism ([Kovacs 2019](#), [Ohno 2008](#)). Based on static mechanistic modeling used to predict DDI ([FDA 2000](#)), no clinically relevant increase in GC exposure is expected with prednisone/prednisolone or HC and tildacerfont. Phase 2 clinical data have shown a low likelihood of a DDI with tildacerfont.

In CAH, a goal of chronic GC replacement therapy is to administer a GC dose that suppresses adrenal androgen overproduction due to ACTH stimulation. Serum A4 is a biochemical marker of adrenal androgen production. A goal of GC therapy is to suppress adrenal androgen production to a level that is at or slightly above the age and sex adjusted normal range (eg, A4 >ULN but <1.25x ULN). An A4 level substantially above the age and sex adjusted ULN is consistent with the GC dose being insufficient to appropriately suppress ACTH-driven adrenal androgen production. An A4 level substantially below the age and sex adjusted ULN is consistent with over-suppression of ACTH-driven adrenal androgen production due to too high of a GC dose.

By modulating ACTH release, it is postulated that tildacerfont will allow a lower daily GC replacement dose, while maintaining control of adrenal androgen production. To test this

hypothesis, A4 levels will be used to monitor the impact of GC replacement therapy on adrenal androgen production.

Another important goal of treatment in CAH is the reduction of adrenal hormone levels. To that end, this study will also measure the effect of tildacerfont on key hormones (ACTH, A4, 17-OHP). Other exploratory efficacy endpoints will assess additional clinical benefit associated with reduction in GC dose and hormone control, such as improvements to QoL, metabolic parameters, and BMD.

The schedule of study visits interspersed with telephone contacts provides an appropriate balance between minimizing subject burden and closely monitoring subjects for safety and response to therapy.

Study drug will be taken with a meal because Phase 1 clinical studies showed that taking tildacerfont in a fed state improves drug absorption. The meal should contain approximately 25-50% fat content because high fat intake with study drug may increase drug accumulation.

Individual treatment-stopping criteria and appropriate laboratory and medical assessments have been established to ensure subject safety.

4.3 Justification for Dose

In Study SPR001-204, tildacerfont tablets will be administered at 200 mg QD for up to 76 weeks. Data from previous Phase 1 and Phase 2 studies support the safety and potential PD effects of this dose.

The safety data show that tildacerfont has been generally well tolerated in all clinical studies to date, with no related SAEs. Specifically, tildacerfont at a dose of ≤ 200 mg/day has been well tolerated in previous clinical studies.

The clinical efficacy/PD data show CRF₁ receptor target engagement (reductions in ACTH) and reductions in key adrenal hormones (17-OHP and A4) in subjects with CAH dosed for 2 weeks with 200 mg/day tildacerfont, the lowest dose previously tested in subjects with CAH (see [Section 2.3.2](#)).

A 1-compartment PK model with first-order absorption and elimination was fit to PK data from Study SPR001-201. This model was then used to estimate the steady-state exposure for each subject at each dose. For each of the 3 key hormones of ACTH, 17-OHP, and A4, an apparent plateau in response is observed at exposures achieved with the 200 mg/day dose of tildacerfont, with no additional benefit at the higher doses. This suggests that a dose of ≤ 200 mg/day tildacerfont may provide maximum benefit while minimizing drug exposure.

The long half-life of tildacerfont, estimated to be approximately 60 hours after single-dose administration, supports QD dosing in this study.

Guided by the safety, efficacy, and exposure-response analyses from available clinical data, Spruce has selected a tildacerfont tablet dose of 200 mg QD for testing in Study SPR001-204. This dose lies within a clinically precedented dose range that has both been well tolerated and produced responses in key hormones.

